The FACT/GOG-Ntx and its peripheral sensory subscale measures the severity on a continuous scale. The FACTGOG-Ntx is a reliable and valid instrument for assessing the impact of neuropathy on health-related quality of life in adults, having demonstrated strong psychometric properties, including sensitivity to meaningful clinical distinctions and responsiveness to change over time patterns were reported by the National Surgical Adjuvant Breast and Bowel Project. (3, 4, 5, 6) Scale scores were related to clinical grading scores non-linearly (i.e., 2.4 for clinical Grade 0 to 24.5 for clinical Grade 3). The scale allowed for discrimination among patients with similar clinical grade and highlighted different symptoms as being bothersome at different points during therapy. As a measure of criterion validity, Huang et al. demonstrated that scale scores were able to discriminate the presence or absence of CIPN, based on clinical grading, with an area under the receiver operating characteristics curve (AUC of ROC) of 81%. (7) CIPN has been shown to have a negative effect on health-related quality of life (HRQL) in several diverse populations. Large effect sizes, equivalent to two standard deviations, were detected in HRQL comparisons between chemotherapy naïve patients and those with CIPN in a study of women with ovarian cancer. (8) Mols et al. demonstrated in a sample of over 1600 patients that those in the top decile of neuropathy symptoms had statistically significant worse HRQL across all measured domains, a finding echoed in the qualitative research of Textor et al. (9, 10)

The FACT/GOG-Ntx also has been used successfully in the ongoing Children's Oncology Group study AHOD 1331 for both youth self-report (patients ages 11 years and older) and parent proxies. Internal consistency reliability exceeded 0.80 for both raters on the 9-item total neuropathy scale score and on the 4-item sensory neuropathy subscale. ([name], personal communication). Additionally, mean scale scores for the FACT-Ntx differed significantly by clinical grading (stratified as any neuropathy vs. no neuropathy) for both raters. Compared to patients without neuropathy, those with neuropathy reported significantly lower HRQL scores, as has been documented in adults with neuropathy.

3. PROMIS Global

The PROMIS-Global is a 10-item measure of general health and functioning, detailing the respondent's perceptions of physical function, pain, fatigue, emotional distress, social health, and overall health. In addition to specific item scores, the measure yields two summary scores for global physical health and global mental health. These summary scores can be compared to general population norms when converted to a T-score metric (mean, 50; SD, 10). Using an established algorithm, this measure can also be used to calculate EQ-5D index scores. (11)

d. Timepoints

The quality of life assessments are scheduled to occur at baseline prior to registration, at Day 56 (corresponding to Day 1 of Cycle 3 [assessment window +/- 7 days]), 4-8 weeks after the last dose of protocol therapy (following last dose of study drug or radiation therapy, whichever is later) [assessment window 4 weeks]), at 1 year after registration (assessment window +/- 7 days), and at 3 years after registration (assessment window +/- 7 days).

e. Experimental Research Techniques/tests Employed and Expertise of PI

Research staff members will be trained to administer quality of life forms by viewing a training module available on the SWOG website ([www.swog.org](http://www.swog.org)); the program can be found at the CRA WorkBench/Training. For example, this training program indicates that research staff should not influence the patient's responses to the questionnaires. Research staff will need to enter the reported data into the online Medidata RAVE system. Efforts to minimize missing data are critical to obtaining interpretable results. The training module addresses methods for reducing missing data.

[name]., M.R.P., Tufts Medical Center, is the Principal Investigator on two ongoing embedded studies within AHOD 1331 (study Chair: [name]., MSc., Emory, Children's Hospital of Atlanta) to evaluate chemotherapy-induced peripheral neuropathy, using the FACT/GOG-Ntx and global HRQL.

Statistical analyses will be performed by [name]., who leads the PRO Core within the SWOG Statistical Center.

f. Recall Period for the measures is as follows:

1. FACT/GOG-Ntx: 7 days
2. PROMIS-Global (adults): 7 questions "in general," 3 questions past 7 days; Pediatric Global: 7 "in general", 2 questions past 7 days
3. Fatigue 7a (adults) OR Fatigue 10a (kids): 7 days

g. QOL Statistical Considerations

Quality of life assessments will occur in conjunction with the clinical follow-up schedule in order to minimize missing data and to link the clinical assessments with patients' self-reported symptom burden. This design should also minimize patient and staff burden. The assessment times are fixed and are scheduled to occur as noted in [Section 18.2d](#). The time points are designed to capture acute toxicity and HRQL impact prior to treatment initiation, during planned therapy (e.g., Cycle 3, Day 1) and at the end of planned therapy (including radiation), as well as the persistence of toxicity and HRQL impact after date of registration (at 12 and 36 months). The assessment at Cycle 3, Day 1 was selected to align with a post 2 cycle disease response that will be done on the trial in the same time frame. The end-of-treatment visit after completion of planned therapy also coincides to the anticipate dose peak level of the tubulin toxins and thus, the potentially greatest risk of CIPN, as has been seen in our ongoing COG study. The 12-month after date of registration time points are important to understanding the potential resolution of acute toxicities and their impact on HRQL for these novel agents. The 36-month after date of registration time point is deliberately chosen both to assess persistence of toxicity (i.e., fatigue and neuropathy), as well as to capture HRQL in cases where salvage therapy may have been necessary in cases of failure of primary treatment on either study arm. In addition, given the unknown temporal course of immune modulation in de novo disease both with regard to control of HL and to the risk of immune-mediated toxicity, a 36-month assessment time point is thought to be important. The specification of fixed assessment times helps limit the potential to induce a dependence between the clinical and QOL outcomes, which could bias the QOL results. Study windows have been created around each of the planned assessments to avoid dependency of the treatment course (e.g., due to treatment delays).

Multiple primary endpoints will be examined, two for fatigue, and two for neuropathy. To examine the four independent endpoints with full power that includes adjustment for multiple comparisons, all 940 eligible patients will be included in the QOL analyses. To adjust for multiple comparisons, we will set alpha=.0125 based on Bonferroni.

Two primary endpoints are specified for fatigue, one 4-8 weeks after the last dose of protocol therapy (following last dose of study drug or radiation therapy, whichever is later) and one at 1 year after randomization. We hypothesize that patients randomly assigned to the N-AVD arm will have worse fatigue scores during initial treatment, although there is uncertainty about the direction of the effect, suggesting that a two-sided design is appropriate. Fatigue is further hypothesized to be mitigated by year 1, although again there is uncertainty regarding the impact of the therapies on the magnitude and direction of the affects at this timepoint. Fatigue will be examined by arm using the PROMIS Fatigue. (12,13,14,15) Both a pediatric and adult version of the PROMIS Fatigue have been validated as noted above and have been determined to assess the same constructs in the different patient age groups (pediatric vs. adults). This allows the combining of scores across age, although stratification by age will be conducted given potentially different levels of fatigue. The PROMIS-Fatigue scale has a standardized mean of 50 with a SD of 10 points. (16,17,18,19) Representative literature about the trajectory of fatigue over time in a broad range of cancer patients indicates that follow-up scores after treatment initiation have a standard deviation of about 12 points. (20) Our goal is to identify an effect size of 0.3, a small to medium effect, with good power. (21) This corresponds to a difference of 3.6 points or larger in the PROMIS-Fatigue between arms, which has been shown to be approximately in the middle of the range (3-5 points) of clinically meaningful differences identified for this instrument. (22) We assume, conservatively, dropout or non-response of 20% at the first assessment (time of completion of treatment) and 25% at the second assessment (1 year after randomization). Based on these parameters and using a two-sided two-arm normal design, there will be 95% power to detect a difference of 3 points in the PROMIS-Fatigue at last day of protocol therapy and 93% power at 1 year after randomization.

Neuropathy will be analyzed by arm at 1 year and at 3 years after randomization. This instrument is validated for both pediatric and adult patients. We hypothesize that patients assigned to the BV-AVD arm will have worse neuropathy over time compared to patients on the N-AVD arm, although as for fatigue, we allow uncertainty about the direction of the effect and will rely on a two-sided design. Neuropathy will be measured using the FACT/GOG-Ntx. The modified 9-item scale FACT/GOG-Ntx measures the severity of neurotoxicity on a continuous scale. A change of 3 points has been proposed as the minimally significant (i.e., clinically important) difference for this subscale. (23) Standard deviations at  $\geq 3$  months after initiation of treatment are generally about 9 points; for design purposes, we assume a more conservative standard deviation of 10 points, corresponding to an effect of 0.3 points, a small to medium effect. (24,25) Greater dropout and non-response of 25% is assumed at 1 year, and 35% at 3 years. Based on these parameters and using a two-sided two-arm normal design with alpha=.0125, there will be 93% power to detect a difference of 3 points in the FACT/GOG-Ntx at 1 year after randomization and 89% at 3 years.

Consistent with the design, the analyses of the PROMIS-Fatigue and FACT/GOG-Ntx endpoints will be conducted using multiple linear regression analysis, adjusting for stratification factors and the baseline score as covariates. See [Section 6.0](#) for stratification factors. We will also conduct longitudinal modeling of the outcome measures over time. Power for the longitudinal analysis will be greater since the addition of all available scores over time will provide more information. For longitudinal modeling, linear mixed models will be used. The potential for

differential dropout by arm will be mitigated by reminder notifications to site investigators to encourage proper assessment and submission of forms at every required time point for all patients. Dropout patterns will be monitored on an ongoing basis. Nonetheless the potential for non-random dropout exists. Cohort plots will be prepared to examine the extent to which missing data are informative (i.e., scores are higher (worse) for patients just before their data are missing for the subsequent assessment). If there is evidence of non-random dropout, pattern-mixture models will be utilized as a sensitivity analysis. Covariates for longitudinal modeling will include intervention assignment, assessment time, their interaction, the baseline score, and the stratification factors as covariates. We will also explore differences in trajectories by categorical age (12-17 years, 18-39 years,  $\geq$  40 years).

Secondary objectives include examinations by arm of fatigue and neuropathy at the other specified discrete timepoints (fatigue: beginning of Cycle 3, and 3 years after randomization; neuropathy: beginning of Cycle 3 and time of completion of treatment). Analyses by arm at these individual assessment times will be conducted using multiple linear regression, adjusting for stratification factors and the baseline score as covariates. For all secondary analyses, no adjustment for multiple comparisons will be made, as these are considered hypothesis-generating, requiring confirmation in independent analysis.

We will also examine patient-reported health-related quality of life by arm using the PROMIS Global for pediatric and adult patients. (26,27,28) Further, we will compare the quality-adjusted survival between the study arms, using the Q-TWiST method from diagnosis to the end of follow up. Utility weights for this analysis will be obtained from the PROMIS-Global, via established crosswalk algorithms. (29)

We will describe scores on all patient-reported measures at each time period using means, standard deviations, medians, 25th-75th percentiles, minimums and maximums, histograms, frequencies, and percentages. Missing data will be explored for all variables.

h. References

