### 6.0 STRATIFICATION FACTORS

Patients will be randomized between Arm 1 – nivolumab + AVD and Arm 2 – brentuximab vedotin + AVD in a 1:1 fashion using a randomized dynamic balancing algorithm with stratification based on:

- a. Age (years): age 12-17 vs. age 18-60 vs. age > 60
- b. International prognostic score: 0-3 vs. 4-7
- c. Pre-specified plan to use Residual PET Radiation Therapy (Residual PET RT)\*: yes vs. no  
\* See [Section 7.5](#).

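### A Holm step-down test of the four primary QOL endpoints would keep the familywise error of the planned Bonferroni test and gain some power; this is a cheap improvement, not the correction of an error

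*Combined protocol and SAP*

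**What the plan says.** Section 18.2g (QOL Statistical Considerations) defines the family: "Multiple primary endpoints will be examined, two for fatigue, and two for neuropathy". The fatigue pair is measured 4-8 weeks after the last dose of protocol therapy and at 1 year; the neuropathy pair at 1 and 3 years. The adjustment is given in one sentence, "To adjust for multiple comparisons, we will set alpha=.0125 based on Bonferroni", and the neuropathy power is computed "using a two-sided two-arm normal design with alpha=.0125". For fatigue the direction is uncertain, "suggesting that a two-sided design is appropriate"; for neuropathy the plan "will rely on a two-sided design".

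The powers are based on the full trial population: "all 940 eligible patients will be included in the QOL analyses". Section 6.0 randomizes "in a 1:1 fashion using a randomized dynamic balancing algorithm", so 470 per arm. The stated powers are 95% and 93% for fatigue, and 93% and 89% for neuropathy.

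Section 18.2g contains no step-down, hierarchical or alpha-recycling rule. Secondary QOL analyses are explicitly unadjusted.

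**The concern.** Single-step Bonferroni holds every endpoint to .0125 whatever happens to the other three. Holm compares the ordered p-values with .05/4 = .0125, .05/3 = .0167, .05/2 = .025 and .05, and stops at the first failure. The smallest p-value faces the Bonferroni threshold and later ones face easier thresholds, so Holm can only add rejections. Its 5% familywise guarantee needs no assumption about correlation. That is useful here because the four endpoints come from the same patients, although Section 18.2g calls them independent.

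What is at stake is power for the second and later rejections. Section 2.5 says that QOL results may inform practice, especially if PFS is similar, and the hypotheses in Section 18.2a cover both fatigue and neuropathy. The endpoint with least power is 3-year neuropathy, with 35% assumed missing, and it is the one that addresses persistence.

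**Working it through.** **Inputs (Sections 6.0 and 18.2g).** 470 per arm; two-sided alpha .0125, so z = 2.498. Fatigue: SD 12, effect size 0.3 = 3.6 points, missing 20% after therapy and 25% at 1 year. Neuropathy: SD 10, difference 3 points (again 0.3 SD), missing 25% at 1 year and 35% at 3 years.

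**Step 1: reproduce the plan.** The implied familywise level is 4 × .0125 = .05. Power = Φ(δ/(σ√(2/n)) − 2.498), with n = 470 × (1 − missing).

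| Endpoint | n per arm | δ/(σ√(2/n)) | Power | Plan |
|---|---|---|---|---|
| Fatigue, after therapy | 376 | 4.113 | 94.7% | 95% |
| Fatigue, 1 year | 352.5 | 3.983 | 93.1% | 93% |
| Neuropathy, 1 year | 352.5 | 3.983 | 93.1% | 93% |
| Neuropathy, 3 years | 305.5 | 3.708 | 88.7% | 89% |

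All four agree, but the fatigue figures need 3.6 points. The fatigue power sentence prints 3 points; at 3 points with SD 12 the formula gives 82.4% and 79.4%. That sentence should be reconciled separately.

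**Step 2: Holm against Bonferroni.** Four correlated normal test statistics were simulated with the means above (1,000,000 draws per scenario, checked with 400,000). The documents give no correlation between endpoints, so exchangeable values of 0, 0.3, 0.5 and 0.7 are assumed. Ranges below run over these values.

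*All four effects at 0.3 SD:*

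| Endpoint | Bonferroni | Holm |
|---|---|---|
| Fatigue, after therapy | 94.7% | 96.9-98.2% |
| Fatigue, 1 year | 93.1% | 96.2-97.6% |
| Neuropathy, 1 year | 93.1% | 96.2-97.6% |
| Neuropathy, 3 years | 88.7% | 94.4-95.6% |
| All four rejected | 73-82% | 90-93% |
| At least one rejected | 98.7% to over 99.9% | identical |

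*Fatigue difference 3 points with SD 12, neuropathy as designed:* fatigue goes from 82/79% to about 90-92/88-90%, and all four from 54-70% to 79-85%.

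*Some effects null:*
- No fatigue effect at 1 year: the other three go from 95/93/89% to about 96-97/95-96/92-93%.
- No fatigue effect at either time: neuropathy goes from 93/89% to 94/90-91%.
- Only 3-year neuropathy real: 88.7% to 88.8%.

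**Step 3: error rate.** With all four effects null, the familywise error is 4.9% (correlation 0) and 4.3% (0.5), the same for both methods. In the mixed-null scenarios tried, Holm stayed at or below 4.8%. In every draw, each Bonferroni rejection was also a Holm rejection.

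**Step 4: timing.** Before the 3-year result exists, count that endpoint as not rejected (equivalent to p = 1). The first three endpoints can then use only .0125, .0167 and .025. With all effects at 0.3 SD and correlation 0, their power is 97/96/96%, against 98/98/98% once the family is complete. Setting a missing p-value to 1 can only remove Holm rejections, so no early rejection is later withdrawn, and the simulation showed none.

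**The case against.** The strongest reply is that nothing is wrong. The family is named, the adjustment is stated and valid, and the powers follow from it once fatigue is taken at 3.6 points. All of that stands: this is a choice between two valid procedures for an embedded QOL objective already planned at 89-95%.

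A reader might infer that Bonferroni throws power away for nothing. The documents do not support that. The endpoints mature after therapy, at 1 year and at 3 years, and Bonferroni allows each to be declared on maturity with no further rule. Holm's later thresholds depend on the whole family. A team reporting at 1 year could mistakenly apply .0167, .025 and .05 to the three available p-values and test the fourth separately; the 5% guarantee would not cover that. A bare change of method name is therefore not enough.

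A reader might also take the rise from 73% to 90% for all four endpoints as the benefit. It requires all four effects to be real. Section 18.2a expects fatigue to resolve by one year post treatment, and Section 18.2g expects it to be mitigated by year 1, though both the size and the direction are left uncertain. The plan nowhere requires all four to be rejected. The marginal gains across scenarios are the fairer summary.

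What survives is that Holm never does worse on rejections, needs no extra patients or visits, and can be given a timing rule that leaves every early claim available today in place.

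**Conclusion.** The point holds as an optional, low-cost improvement. At the design effects, Holm adds about 2 to 4 percentage points for the first three endpoints and 6 to 7 points for 3-year neuropathy (88.7% to 94.4-95.6%), at the same 5% familywise error. If fatigue differs by the printed 3 points with SD 12, fatigue gains about 7 to 11 points. With fatigue null at both times, neuropathy gains about 1 to 2 points; with a single real effect, almost nothing. Power to reject at least one endpoint never changes.

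The dominance of Holm over Bonferroni and its error control rest on no assumption about correlation. The sizes rest on normal test statistics, the plan's SDs and missing rates, and an assumed exchangeable correlation of 0 to 0.7. The plan contains no invalid test on this point, and its stated QOL conclusions would not be compromised by leaving Bonferroni in place.

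**What to change.** Replace the Bonferroni sentence in Section 18.2g with:

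> The four primary QOL endpoints will be tested by the Holm step-down procedure at a familywise two-sided alpha of .05. An endpoint with p<=.0125 may be declared when it matures. In any analysis before the 3-year neuropathy result is available, that endpoint is counted as not rejected, so the ordered p-values of the available endpoints are compared with .0125, .0167 and .025; the full procedure is completed when the 3-year result is available.

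Keep .0125 as the planning level, so that the powers derived from it become lower bounds and the sample-size text is unchanged by this amendment. Make the change before any QOL endpoint is compared by arm.

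The change costs no patients, visits or type I error. It has three downsides: part of the gain waits for the 3-year data; an endpoint reported as non-significant earlier may become significant then; and step-down decisions do not match single-step simultaneous confidence intervals one-for-one. Section 18.2g specifies no such intervals at present, so if they are wanted they must be added.

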- All contrast-enhanced CT images of chest, abdomen and pelvis (+ neck or other involved areas, if involvement at baseline) (or if contraindicated, PET-CT, CT, MRI, or MR-PET) from scans performed to assess disease as specified in [Section 15.4](#). Submit to IROC Ohio (via TRIAD strongly preferred) for retrospective central imaging review.
  - For patients who have had 1-year and 2-year after registration contrast-enhanced CT (or if contra-indicated, PET-CT, CT,

MRI, or MR-PET) scan performed prior to activation of S1826 Protocol Revision 6, submit images to IROC Ohio within 60 days after participating site activation of S1826 Protocol Revision 6 (Version Date 9/2/2023).

- If CT scan is contraindicated and PET-CT scan is submitted, S1826 Imaging Adjunctive Data Sheet for PET scans is required. This form is submitted electronically via the IROC website at: [https://wrightcenterofinnov.qualtrics.com/fe/form/SV\\_cCOPih8vSYcCnfU](https://wrightcenterofinnov.qualtrics.com/fe/form/SV_cCOPih8vSYcCnfU). See Section 14.4a for navigation instructions. See Section 14.4a for navigation instructions.

g. WITHIN 15 DAYS AFTER CYCLE 3, DAY 1:

Submit the following:

- Specimens as outlined in [Section 15.2](#).
- **S1826** Pediatric PROMIS Global Health 7+2 (Pediatric) or S1826 PROMIS-Global Health (Adults)
- **S1826** Pediatric PROMIS Fatigue 10a (Pediatrics) or **S1826** PROMIS Fatigue 7a (Adults)
- **S1826** FACT/GOG-Ntx (Pediatrics and Adults)
- **S1826** Cover Sheet for Patient-Completed Questionnaires or **S1826** Cover sheet for Pediatric Patient-Completed Questionnaires.

h. WITHIN 15 DAYS AFTER LAST DOSE OF PROTOCOL THERAPY (following last dose of study drug or radiation therapy, whichever is later):

Submit the following:

- Vital Status Form
- Off Treatment Notice
- **S1826** Treatment Form
- **S1826** Adverse Event Form
- **S1826** Pediatric PROMIS Global Health 7+2 (Pediatric) or **S1826** PROMIS-Global Health (Adults)
- **S1826** Pediatric PROMIS Fatigue 10a (Pediatrics) or **S1826** PROMIS Fatigue 7a (Adults)
- **S1826** FACT/GOG-Ntx (Pediatrics and Adults)
- **S1826** Cover Sheet for Patient-Completed Questionnaires or **S1826** Cover sheet for Pediatric Patient-Completed Questionnaires.

i. WITHIN 15 DAYS AFTER THE END OF TREATMENT VISIT (4-8 weeks after last dose of study drug):

Submit the following:

- Vital Status Form
- **S1826** Adverse Event Form
- **S1826** Concomitant Medication Form
- Follow-up Tumor Assessment Form

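### The 95%/93% fatigue power in Section 18.2g fits 3.6 points, not the printed 3; separately, Section 14.4h makes the end-of-therapy QOL forms due before their assessment window opens

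*Combined protocol and SAP*

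**What the plan says.** **Power.** Section 18.2g names four primary QOL endpoints, two for fatigue and two for neuropathy, and splits alpha across them: "To adjust for multiple comparisons, we will set alpha=.0125 based on Bonferroni". All 940 eligible patients enter the QOL analyses. The fatigue paragraph gives two standard deviations. One is the scale norm: "The PROMIS-Fatigue scale has a standardized mean of 50 with a SD of 10 points". The other is for patients on follow-up: "follow-up scores after treatment initiation have a standard deviation of about 12 points". It sets the goal at an effect size of 0.3 and converts it: "This corresponds to a difference of 3.6 points or larger in the PROMIS-Fatigue between arms". It describes 3-5 points as the clinically meaningful range. It assumes 20% loss at the end-of-therapy assessment and 25% at one year, and uses a two-sided two-arm normal design. It then concludes that "there will be 95% power to detect a difference of 3 points in the PROMIS-Fatigue at last day of protocol therapy and 93% power" at one year.

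The planned analysis of the fatigue and neuropathy endpoints "will be conducted using multiple linear regression analysis, adjusting for stratification factors and the baseline score as covariates".

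**Timing.** The fatigue paragraph opens by placing the first endpoint 4-8 weeks after the final dose of protocol therapy, meaning study drug or radiation, whichever ends later. Sections 15.5b and 18.2d say the same. Section 14.4h is headed "WITHIN 15 DAYS AFTER LAST DOSE OF PROTOCOL THERAPY (following last dose of study drug or radiation therapy, whichever is later" and lists PROMIS Global, PROMIS Fatigue, FACT/GOG-Ntx and the questionnaire cover sheet among the forms due by then.

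**The concern.** The power sentence says it follows from the parameters just listed, but it prints a smaller difference than the one those parameters were built on. Three points is the bottom of the plan's own meaningful range and 3.6 is the chosen target, so the two are not interchangeable. A reader interpreting a null fatigue result would credit the trial with a 5% or 7% chance of missing a true 3-point difference, when the stated inputs imply far more. This affects two of the four primary QOL endpoints.

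The same sentence also places the first fatigue endpoint on the final day of protocol therapy, although the paragraph opens by defining it as 4-8 weeks later.

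The form deadline is a separate matter at the same timepoint. If forms are due before the assessment window opens, a site cannot meet both rules. It must either submit late or collect early. Early collection is a possible consequence, not an established one.

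**Working it through.** **Inputs (Sections 11.3 and 18.2g).** 470 eligible patients per arm. Two-sided alpha 0.0125, so the critical value is z = 2.498. Loss of 20% and 25% leaves n = 470 × 0.80 = 376 and 470 × 0.75 = 352.5 per arm. SD is 12.

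**Formula.** Power = Φ(δ/SD × √(n/2) − 2.498).

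**Check of the method on the neuropathy figures.** Section 18.2g prints 93% at one year and 89% at three years for 3 points, SD 10, with 25% and 35% loss (n = 352.5 and 305.5). The formula gives 93.1% and 88.7%, so it reproduces the plan's own calculation.

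**Fatigue.**

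| Difference | SD | End of therapy (n = 376) | 1 year (n = 352.5) |
|---|---|---|---|
| Printed: 3 points | – | 95% | 93% |
| 3.6 points | 12 | 94.7% | 93.1% |
| 3 points | 12 | 82.4% | 79.4% |
| 3 points | 10 | 94.7% | 93.1% |

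For example, at 3 points and SD 12 with n = 376: 0.25 × √188 − 2.498 = 0.930, and Φ(0.930) = 0.824. At 3.6 points: 0.30 × √188 − 2.498 = 1.616, and Φ(1.616) = 0.947.

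The miss rates at 3 points are therefore 1 − 0.824 = 17.6% and 1 − 0.794 = 20.6%.

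**Other readings of the design at 3 points, SD 12.** None gives both printed figures:
- t-based: 82.2% / 79.2%
- one-sided 0.0125: 88.2% / 85.9%
- two-sided 0.05: 92.9% / 91.3%
- one-sided 0.05: 96.3% / 95.3%
- no dropout: 90.9%
- 987 enrolled, with dropout: 84.5% / 81.7%

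**What 3 points would need.** Setting SD = 3/[(2.498 + z_power) × √(2/n)] gives 9.93 for 95% and 10.02 for 93%. If the raw SD is 12 and baseline adjustment supplies the reduction, the correlation needed is r = √(1 − (SD/12)²) = 0.56 and 0.55. The documents give no correlation. Over an assumed range, with SD replaced by 12√(1 − r²):

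| Assumed r | End of therapy | 1 year |
|---|---|---|
| 0.3 | 86.3% | 83.7% |
| 0.5 | 92.8% | 90.9% |
| 0.6 | 96.3% | 95.1% |

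**Timing.** Both clocks start at the last dose of protocol therapy.
- Section 14.4h: due by day 15.
- Sections 15.5b and 18.2d: assessment from day 28 to day 56.
- Gap: 28 − 15 = 13 days. If the ±7 days in Section 15.5 could open the window at day 21, the gap would still be 21 − 15 = 6 days.

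No other item in Section 14.4 covers this timepoint. Item b is baseline, g is Cycle 3, and o is years 1 and 3. Item i does follow a 4-8 week visit, but it lists no QOL forms and counts from study drug, so it would not cover a patient who goes on to radiation.

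**The case against.** The strongest reply on power is that this is a one-number slip without design consequence. The goal of 3.6 points is printed in the same paragraph, the stated power is right for that goal, and the 940 patients come from the PFS design rather than from this calculation. That stands: nothing in the design was sized on the wrong figure.

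The slip could instead lie in the SD. Three points with SD 10 is also an effect size of 0.3 and gives the same power; 10 is both the scale norm and the neuropathy design SD. This cannot be excluded, but it contradicts the SD of 12 from which the 3.6 points were derived, so the paragraph is inconsistent on either reading.

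The planned regression adjusts for baseline and may recover power. That is also fair, and it is why 82%/79% must be labelled unadjusted. But the power sentence specifies a plain two-arm normal design, and no correlation is offered.

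On timing, it can be said that the assessment time is clear throughout the protocol and only the data-entry deadline is off. That is largely right. The 6-day figure is weak, because Section 18.2d gives this timepoint its own 4-week window and does not say that ±7 days extends it; 13 days is the supported gap. Only fatigue is primary at this assessment. Neuropathy there is secondary ("neuropathy: beginning of Cycle 3 and time of completion of treatment"). None of this makes the two rules compatible.

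**Conclusion.** Both points hold. On the plan's stated inputs, the printed 95%/93% is the power for 3.6 points. For the printed 3 points, unadjusted power is 82.4% at end of therapy and 79.4% at one year, so a true 3-point difference would be missed about 18% and 21% of the time rather than 5% and 7%. This rests on SD 12, two-sided alpha 0.0125, the stated losses and no baseline adjustment. Adjustment could close the gap, but only with a correlation near 0.55 that the plan would have to state. Power for the 3.6-point goal is correct.

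Separately, the Section 14.4h deadline falls 13 days before the assessment window in Sections 15.5b and 18.2d opens, so the forms cannot be both on time and in window. The final-day label in the power sentence adds to the ambiguity about when this endpoint is measured. These are corrections that should be made; they do not threaten the trial's design.

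**What to change.** 1. In the Section 18.2g fatigue power sentence, change 3 points to 3.6 points, or keep 3 points and give 82%/79% as unadjusted power. If baseline adjustment is relied on, state the assumed correlation.
2. In the same sentence, replace the wording that puts the first endpoint on the final day of therapy with the 4-8 week timepoint defined at the start of the paragraph.
3. In Section 14.4, take the PROMIS Global, PROMIS Fatigue, FACT/GOG-Ntx and questionnaire cover sheet lines out of item h. List them as a new item due within 15 days after the QOL assessment held 4-8 weeks after study drug or radiation ends, whichever is later. The Vital Status Form, Off Treatment Notice, Treatment Form and Adverse Event Form keep the current item h deadline.

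The cost is one number, one phrase and four relocated form lines. Sample size, alpha, endpoints, assessment schedule and analysis are unchanged.
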